12.5.1. Definition of Adverse Events

Adverse Event Definition:

- An AE is any untoward medical occurrence in a patient or clinical investigation subject, temporally associated with the use of a medicinal product, whether or not considered related to the medicinal product.
- **NOTE:** An AE can therefore be any unfavorable and unintended sign (including an abnormal laboratory finding), symptom, or disease (new or exacerbated) temporally associated with the use of a medicinal product.

Events meeting AE definition include:

- Any abnormal laboratory test results (hematology, clinical chemistry, or urinalysis) or other safety assessments (e.g., ECGs, radiological scans, vital signs measurements), including those that worsen from baseline, and felt to be clinically significant in the medical and scientific judgement of the investigator.
- Exacerbation of a chronic or intermittent pre-existing condition including either an increase in frequency and/or intensity of the condition.
- New conditions detected or diagnosed after study treatment administration even though it may have been present prior to the start of the study.
- Signs, symptoms, or the clinical sequelae of a suspected interaction.
- Signs, symptoms, or the clinical sequelae of a suspected overdose of either study treatment or a concomitant medication (overdose per se will not be reported as an AE/SAE unless this is an intentional overdose taken with possible suicidal/self-harming intent. This should be reported regardless of sequelae).
- "Lack of efficacy" or "failure of expected pharmacological action" per se will not be reported as an AE or SAE. However, the signs and symptoms and/or clinical sequelae resulting from lack of efficacy will be reported if they fulfil the definition of an AE or SAE.

Events NOT meeting definition of an AE include:

- Any clinically significant abnormal laboratory findings or other abnormal safety assessments which are associated with the underlying disease, unless judged by the investigator to be more severe than expected for the subject's condition.
- The disease/disorder being studied or expected progression, signs, or symptoms of the disease/disorder being studied, unless more severe than expected for the subject's

condition.

- Medical or surgical procedure (e.g., endoscopy, appendectomy): the condition that leads to the procedure is an AE.
- Situations where an untoward medical occurrence did not occur (social and/or convenience admission to a hospital).
- Anticipated day-to-day fluctuations of pre-existing disease(s) or condition(s) present or detected at the start of the study that do not worsen.

12.5.2. Definition of Serious Adverse Events

If an event is not an AE per definition above, then it cannot be an SAE even if serious conditions are met (e.g., hospitalization for signs/symptoms of the disease under study, death due to progression of disease, etc).

Serious Adverse Event (SAE) is defined as any untoward medical occurrence that, at any dose:

a. Results in death

b. Is life-threatening

NOTE: The term 'life-threatening' in the definition of 'serious' refers to an event in which the subject was at risk of death at the time of the event. It does not refer to an event, which hypothetically might have caused death, if it were more severe.

c. Requires hospitalization or prolongation of existing hospitalization NOTE:

- In general, hospitalization signifies that the subject has been detained (usually involving at least an overnight stay) at the hospital or emergency ward for observation and/or treatment that would not have been appropriate in the physician's office or out-patient setting. Complications that occur during hospitalization are AEs. If a complication prolongs hospitalization or fulfills any other serious criteria, the event is serious. When in doubt as to whether "hospitalization" occurred or was necessary, the AE should be considered serious.
- Hospitalization for elective treatment of a pre-existing condition that did not worsen from baseline is not considered an AE.

d. Results in disability/incapacity

NOTE:

- The term disability means a substantial disruption of a person's ability to conduct normal life functions.
- This definition is not intended to include experiences of relatively minor medical significance such as uncomplicated headache, nausea, vomiting, diarrhea, influenza,

and accidental trauma (e.g. sprained ankle) which may interfere or prevent everyday life functions but do not constitute a substantial disruption.

e. Is a congenital anomaly/birth defect

f. Other situations:

- Medical or scientific judgment should be exercised in deciding whether reporting is appropriate in other situations, such as important medical events that may not be immediately life-threatening or result in death or hospitalization but may jeopardize the subject or may require medical or surgical intervention to prevent one of the other outcomes listed in the above definition. These should also be considered serious.
- Examples of such events are invasive or malignant cancers, intensive treatment in an emergency room or at home for allergic bronchospasm, blood dyscrasias or convulsions that do not result in hospitalization, or development of drug dependency or drug abuse.

g. Is associated with liver injury and impaired liver function defined as:

- ALT \geq 3xULN and total bilirubin* \geq 2xULN (>35% direct), or
- ALT \geq 3xULN and INR** \geq 1.5.
- * Serum bilirubin fractionation should be performed if testing is available; if unavailable, measure urinary bilirubin via dipstick. If fractionation is unavailable and ALT \geq 3xULN and total bilirubin \geq 2xULN, then the event is still to be reported as an SAE.
- ** INR testing not required per protocol and the threshold value does not apply to subjects receiving anticoagulants. If INR measurement is obtained, the value is to be recorded on the SAE form.
- Refer to Section 12.2 Appendix 2 for the required liver chemistry follow-up instructions

12.5.3. Definition of Cardiovascular Events

Cardiovascular Events (CV) Definition:

Investigators will be required to fill out the specific CV event page of the eCRF for events that represent the following AEs and SAEs:

- Myocardial infarction/unstable angina
- Congestive heart failure
- Arrhythmias
- Valvulopathy
- Pulmonary hypertension

- Cerebrovascular events/stroke and transient ischemic attack
- Peripheral arterial thromboembolism
- Deep venous thrombosis/pulmonary embolism
- Revascularization

12.5.4. Recording of AEs and SAEs

AEs and SAE Recording:

- When an AE/SAE occurs, it is the responsibility of the investigator to review all
 documentation (e.g., hospital progress notes, laboratory, and diagnostics reports)
 relative to the event.
- The investigator will then record all relevant information regarding an AE/SAE in the eCRF
- It is **not** acceptable for the investigator to send photocopies of the subject's medical records to GSK in lieu of completion of the GSK, AE/SAE eCRF page.
- There may be instances when copies of medical records for certain cases are requested by GSK. In this instance, all subject identifiers, with the exception of the subject number, will be blinded on the copies of the medical records prior to submission of to GSK.
- The investigator will attempt to establish a diagnosis of the event based on signs, symptoms, and/or other clinical information. In such cases, the diagnosis will be documented as the AE/SAE and not the individual signs/symptoms.

12.5.5. Evaluating AEs and SAEs

Assessment of Intensity

The investigator will make an assessment of intensity for each AE and SAE reported during the study and will assign it to one of the following categories:

- Mild: An event that is easily tolerated by the subject, causing minimal discomfort and not interfering with everyday activities.
- Moderate: An event that is sufficiently discomforting to interfere with normal everyday activities.
- Severe: An event that prevents normal everyday activities an AE that is assessed as severe will not be confused with an SAE. Severity is a category utilized for rating the intensity of an event; and both AEs and SAEs can be assessed as severe.
- An event is defined as 'serious' when it meets at least one of the pre-defined outcomes as described in the definition of an SAE.

Assessment of Causality

• The investigator is obligated to assess the relationship between study treatment and the occurrence of each AE/SAE.

CONFIDENTIAL

- A "reasonable possibility" is meant to convey that there are facts/evidence or arguments to suggest a causal relationship, rather than a relationship cannot be ruled out.
- The investigator will use clinical judgment to determine the relationship.
- Alternative causes, such as natural history of the underlying diseases, concomitant therapy, other risk factors, and the temporal relationship of the event to the study treatment will be considered and investigated.
- The investigator will also consult the Investigator Brochure (IB) and/or Product Information, for marketed products, in the determination of his/her assessment.
- For each AE/SAE the investigator must document in the medical notes that he/she has reviewed the AE/SAE and has provided an assessment of causality.
- There may be situations when an SAE has occurred and the investigator has minimal information to include in the initial report to GSK. However, it is very important that the investigator always make an assessment of causality for every event prior to the initial transmission of the SAE data to GSK.
- The investigator may change his/her opinion of causality in light of follow-up information, amending the SAE data collection tool accordingly.
- The causality assessment is one of the criteria used when determining regulatory reporting requirements.

Follow-up of AEs and SAEs

- The investigator is obligated to perform or arrange for the conduct of supplemental measurements and/or evaluations as may be indicated or as requested by GSK to elucidate as fully as possible the nature and/or causality of the AE or SAE.
- The investigator is obligated to assist. This may include additional laboratory tests or investigations, histopathological examinations or consultation with other health care professionals.
- If a subject dies during participation in the study or during a recognized follow-up period, the investigator will provide GSK with a copy of any post-mortem findings, including histopathology.
- New or updated information will be recorded in the originally completed eCRF.
- The investigator will submit any updated SAE data to GSK within the designated reporting time frames.

12.5.6. Reporting of SAEs to GSK

SAE reporting to GSK via electronic data collection tool

• Primary mechanism for reporting SAEs to GSK will be the electronic data collection tool.

CONFIDENTIAL

- If the electronic system is unavailable for greater than 24 hours, the site will use the paper SAE data collection tool and fax it to the PPD Safety Hotline.
- Site will enter the serious adverse event data into the electronic system as soon as it becomes available.
- After the study is completed at a given site, the electronic data collection tool (e.g., InForm system) will be taken off-line to prevent the entry of new data or changes to existing data.
- If a site receives a report of a new SAE from a study subject or receives updated data on a previously reported SAE after the electronic data collection tool has been taken off-line, the site can report this information on a paper SAE form and fax it to the PPD Safety Hotline or to the Medical Monitor by telephone.
- Contacts for SAE receipt can be found at the beginning of this protocol on the Medical Monitor/Sponsor Information Page.

12.6. Appendix 6: Female Eligibility Criteria

2015N241222 01

A female subject is eligible to participate if she is not pregnant (as confirmed by a negative serum hCG test for females of reproductive potential only), not breastfeeding, or at least one of the following conditions applies:

- Reproductive potential and agrees to follow one of the options listed in the GSK Modified List of Highly Effective Methods for Avoiding Pregnancy in FRP (see below) from 30 days prior to the first dose of study treatment and until seven days after the last dose of study treatment and completion of the follow-up visit.
- Non-reproductive potential defined as either:
 - Pre-menopausal with one of the following: (i) documented tubal ligation; (ii) documented hysteroscopic tubal occlusion procedure with follow-up confirmation of bilateral tubal occlusion; (iii) hysterectomy; or (iv) documented bilateral oophorectomy, or;
 - o Postmenopausal defined as 12 months of spontaneous amenorrhea and age appropriate (i.e. >50 years). In questionable cases, a blood sample with simultaneous FSH and estradiol consistent with menopause is confirmatory (FSH 23.0-116.3 mIU/mL and estradiol ≤10 pg/mL (or ≤37 pmol/L) is confirmatory). Females on hormone replacement therapy (HRT) and whose menopausal status is in doubt will be required to use one of the highly effective contraception methods if they wish to continue their HRT during the study. Otherwise, they must discontinue HRT to allow confirmation of post-menopausal status prior to study enrolment.

12.6.1. Modified List of Highly Effective Methods for Avoiding Pregnancy in Females of Reproductive Potential (FRP)

This list does not apply to FRP with same sex partners, when this is their preferred and usual lifestyle or for subjects who are and will continue to be abstinent from penile-vaginal intercourse on a long term and persistent basis.

- Contraceptive subdermal implant that meets effectiveness criteria including a <1% rate of failure per year, as stated in the product label.
- Intrauterine device or intrauterine system that meets effectiveness criteria including a <1% rate of failure per year, as stated in the product label [Hatcher, 2011]
- Combined estrogen and progestogen oral contraceptive [Hatcher, 2011]
- Injectable progestogen [Hatcher, 2011]
- Contraceptive vaginal ring [Hatcher, 2011]

- Percutaneous contraceptive patches [Hatcher, 2011]
- Male partner sterilization prior to the female subject's entry into the study, and this male is the sole partner for that subject [Hatcher, 2011]. The documentation on the male sterility can come from the site personnel's review of subject's medical records, medical examination and/or semen analysis, or medical history interview provided by her or her partner.

These allowed methods of contraception are only effective when used consistently, correctly and in accordance with the product label.

The investigator is responsible for ensuring that subjects understand how to properly use these methods of contraception.

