4. STUDY DESIGN

4.1. Overall Design

This is a randomized, double-blinded, dose-ranging, placebo-controlled, parallel group study. There is a 28-day Screening period, a 29-day Treatment period, and a Follow-up visit 14 ± 3 days after completing treatment. The study design is outlined in Figure 1.

Figure 1 Study Design

This will be a double-blinded study. The subjects, investigator and sponsor will not be aware of the treatment received.

Subjects will be stratified by prior ESA dose based on the average weekly (for epoetins or darbepoetin) or monthly (for methoxy PEG-epoetin beta) dosing during the 12 weeks prior to randomization (Day 1) as follows:

- Low ESA dose: <100 IU/kg/week epoetin OR <0.5 μg/kg/week darbepoetin OR
 <0.6 μg/kg/week methoxy PEG-epoetin beta
- High ESA dose: ≥100 IU/kg/week epoetin OR ≥0.5 µg/kg/week darbepoetin OR
 ≥0.6 µg/kg/week methoxy PEG-epoetin beta

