- 20. **Other conditions:** Any other condition, clinical or laboratory abnormality, or examination finding that the investigator considers would put the subject at unacceptable risk, which may affect study compliance or prevent understanding of the aims or investigational procedures or possible consequences of the study.
- 21. **Females ONLY:** Does not meet the female eligibility criteria (Section 12.6 Appendix 6), is pregnant [as confirmed by a positive serum human chorionic gonadotrophin (hCG) test for females of reproductive potential (FRP) only], breastfeeding, and if of reproductive potential does not agree to follow one of the options listed in Section 12.6.1.

DIAGNOSTIC ASSESSMENTS AND OTHER CRITERIA

(To be verified on Day -28 only)

- 22. **Vitamin B₁₂:** At or below the lower limit of the reference range (may rescreen in a minimum of 8 weeks).
- 23. Folate: <2.0 ng/mL (4.5 nmol/L) (may rescreen in a minimum of 4 weeks).
- 24. **Ferritin:** <100 ng/mL (<100 µg/L).
- 25. Transferrin saturation (TSAT): <20%.

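### Appendix 6 joins the pregnancy and contraception conditions with *or* instead of *and*, and exclusion 21 corrects this only if its ambiguous list is read as separate grounds

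*Protocol*

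**What the plan says.** Two passages of the protocol set the entry rule for women.

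- **Section 12.6 (Appendix 6)** opens: "A female subject is eligible to participate if she is not pregnant". After a parenthesis on the serum hCG test it continues: "not breastfeeding, or at least one of the following conditions applies". Two conditions follow. The first is "Reproductive potential and agrees to follow one of the options listed in the GSK Modified List of Highly Effective Methods"; the second begins "Non-reproductive potential defined as either" and defines surgical or menopausal status.
- **Section 5.3, exclusion 21** applies to a woman who "Does not meet the female eligibility criteria (Section 12.6 Appendix 6), is pregnant" (again by serum hCG), and ends "breastfeeding, and if of reproductive potential does not agree to follow one of the options listed in Section 12.6.1".

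The seven inclusion criteria in Section 5.2 contain nothing on pregnancy, breastfeeding or contraception, so Appendix 6 takes effect only through exclusion 21. The word *any* at the head of Section 5.3 governs the numbered criteria; it does not say how the elements inside one criterion combine.

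Elsewhere the protocol treats pregnancy as incompatible with study drug. Section 5.6.1 makes pregnancy, or the intention to become pregnant, a reason for permanent discontinuation. Section 7.4.2 repeats this for pregnancy, and Section 12.6.2 adds withdrawal from the study. In the Time and Events Table the only serum pregnancy test before first dose is at Week -2. The list of specific changes under Amendment 01 shows no change to either eligibility passage.

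**The concern.** The *or* in Appendix 6 turns two requirements that should both hold into alternatives. A woman can qualify because she is neither pregnant nor breastfeeding, whatever she does about contraception. She can also qualify on the contraception or non-reproductive-potential condition, whatever her pregnancy or breastfeeding status.

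This matters because Section 5 allows no deviation from the entry criteria and calls adherence to them as specified essential, so the text has to be usable as it stands. With no pregnancy test scheduled on Day 1, the contraception requirement also carries weight between Week -2 and first dose. A site that turns to Appendix 6 for the definition finds a rule at odds with what exclusion 21 appears to intend.

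**Working it through.** The protocol gives no figure to reproduce here. The check is a truth table over four yes/no facts: pregnant (P), breastfeeding (B), of reproductive potential (R), and agrees to a listed contraceptive method (C). That gives 2 × 2 × 2 × 2 = 16 combinations. Dropping the 4 in which a woman is pregnant but not of reproductive potential leaves 12 profiles. The exemptions in Section 12.6.1 (same-sex partners, long-term abstinence) are set aside because they do not bear on the connectives.

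Let *cond* = (R and C) or (not R), the two bulleted conditions of Appendix 6.

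**Step 1. Appendix 6 as written.** The sentence can be parsed in two ways.

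- (not P and not B) or *cond*: this fails only when R holds, C does not, and the woman is pregnant or breastfeeding or both. That is 3 profiles, so 12 − 3 = 9 are eligible.
- not P or not B or *cond*: this fails only when P, B and R all hold and C does not. That is 1 profile, so 12 − 1 = 11 are eligible.

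**Step 2. Appendix 6 with *and*.** (not P) and (not B) and *cond* leaves 3 eligible profiles, none of them pregnant, breastfeeding, or of reproductive potential without agreed contraception. The *or* therefore lets in 9 − 3 = 6 further profiles on the first parse and 11 − 3 = 8 on the second.

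**Step 3. Exclusion 21.** Its elements are: fails Appendix 6; P; B; and (R and not C).

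- Cumulative (all must hold): 1 of 12 profiles is excluded and 11 are not.
- Separate grounds (any one suffices): 9 of 12 are excluded and 3 are not. These are the same 3 as in step 2, and the result does not depend on how Appendix 6 is worded.

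The cases of interest, which come out the same under both parses of Appendix 6:

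| Profile | Appendix 6 as written | Exclusion 21, cumulative | Exclusion 21, separate grounds |
|---|---|---|---|
| Fertile, not pregnant, not breastfeeding, no agreed contraception | eligible | not excluded | excluded |
| Pregnant, not breastfeeding, agrees to contraception | eligible | not excluded | excluded |
| Breastfeeding, fertile, not pregnant, agrees to contraception | eligible | not excluded | excluded |
| Breastfeeding, not of reproductive potential | eligible | not excluded | excluded |
| Pregnant, breastfeeding, no agreed contraception | not eligible | excluded | excluded |
| Fertile, not pregnant, not breastfeeding, agrees to contraception | eligible | not excluded | not excluded |

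**Step 4. Does correcting one passage suffice?** If only Appendix 6 is corrected, the cumulative reading of exclusion 21 still excludes 1 of 12. If only exclusion 21 is clarified, entry is decided correctly, but Appendix 6 goes on calling eligible women whom exclusion 21 excludes. Both passages need the edit if they are to agree.

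**The case against.** The strongest reply is that exclusion 21 already does the job. Its own wording counts against a cumulative list. A pregnant woman is necessarily of reproductive potential, so if pregnancy were already required, the qualifier *if of reproductive potential* would do no work. A rule that excluded only a woman who is pregnant, breastfeeding and refusing contraception all at once is not one a site would apply. Read as separate grounds, the criterion stops every woman in the first four rows of the table. Exclusion 20 also lets the investigator exclude for unacceptable risk, and dosing a woman with a known positive test would run against Sections 5.6.1 and 7.4.2.

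Most of this stands. A reader might infer that the protocol as a whole admits pregnant women, or that neither passage corrects the other. The documents support that only on the strained reading of exclusion 21. What remains is that Appendix 6 is wrong on its face, and that the one criterion giving it effect has to be interpreted before it corrects the error.

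Two further inferences are tempting and should not be drawn.

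- *That the contraception lead cannot be met.* Appendix 6 asks for contraception "from 30 days prior to the first dose of study treatment and until seven days after the last dose", and Section 4.1 says "There is a 28-day Screening period". But Section 4.2 makes 28 days a minimum and allows visits to move by 2 days either way. A first visit at Day -30 gives exactly 30 days, and contraception already in use meets the requirement. A look-back longer than screening is not in itself a contradiction; other entry criteria have one.
- *That a wrongly admitted woman would leave no recorded deviation.* SAP Section 4.1 takes the eligibility-deviation summary from an eCRF page that is not in the documents, and SAP Section 11.1.1 refers important deviations to a separate rules document. How such a case would be coded cannot be determined from what is available.

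**Conclusion.** The point holds as a drafting error in an operative, safety-relevant entry rule. Read literally, Appendix 6 makes eligible a fertile woman without contraception and a pregnant or breastfeeding woman who agrees to it, under either parse of the sentence. This contradicts the evident intent of exclusion 21 and the pregnancy provisions in Sections 5.6.1, 7.4.2 and 12.6.2. Exclusion 21 is ambiguous rather than plainly wrong.

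The practical risk is well below what the literal logic suggests, because the natural reading of exclusion 21 and the Week -2 test would probably catch most cases. Only women fall under these criteria, and the contraception element concerns only those of reproductive potential. They are likely to be few among about 90 randomized subjects, although the documents give no count and that is an assumption. Sample size and the primary dose-response analysis are unaffected. The conclusion also assumes that the pregnancy provisions show the intended rule, which the sponsor can readily confirm.

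**What to change.** Make two wording changes together in the next amendment, after the sponsor confirms the intent.

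1. In Appendix 6, change *or at least one* to *and at least one*, so that not being pregnant, not breastfeeding, and meeting one of the two conditions are all required.
2. In exclusion 21, join the grounds with *or*: fails Appendix 6; or is pregnant; or is breastfeeding; or is of reproductive potential and does not agree to an option in Section 12.6.1. Each ground then excludes by itself, and the criterion matches the appendix.

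The exemptions in Section 12.6.1 can stay as they are. The cost is a few words. No procedure, visit, test or analysis changes.
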